2.1. Study Design

This is a single arm, single stage phase II study to evaluate the efficacy of oral ABT-888 in combination with TMZ for the treatment of metastatic breast cancer. Subjects will receive ABT-888, 30mg PO/dose, every 12 hours on days 1 through 7 of each 28 day cycle. For cycle 1, TMZ will be started at a dose of 150mg/m²/day PO, daily on days 1 through 5 of a 28 day cycle. Measurable tumor will be assessed for response every 8 weeks by standard Response Evaluation Criteria In Solid Tumors. Additional study endpoints include safety assessment and evaluation of clinical benefit rate (CR+PR+SD>16 weeks) and progression free survival. Exploratory correlative studies will also be conducted as described in section 9.1.

This study will be conducted within the Dana-Farber/Harvard Cancer Center only.

A total enrollment of 41 patients is planned. However, patients who enter the study but do not complete 1 cycle of study drugs will not count towards this accrual goal of 41, so a few more patients may be entered.

The study is intended to complete accrual in approximately 18 months with an accrual rate of 2.5 subjects per month.

An expansion cohort of 20 patients with BRCA1 or BRCA2 mutations is planned. Patients who enter the study but do not complete 1 cycle of study drugs will not count towards this accrual goal of 20, so a few more patients may be entered. The expansion cohort is intended to complete accrual in approximately 4 months with an accrual rate of 5 patients per month.

2.2. Primary Objectives (for the primary study and an expansion cohort of BRCA1/2 positive patients)

- To determine the objective response rate (ORR) of ABT-888 and TMZ in metastatic breast cancer.

2.3. Secondary Objectives (for the primary study and an expansion cohort of BRCA1/2 positive patients)

- To further characterize the safety and tolerability of ABT-888 and TMZ in patients with metastatic breast cancer
- To evaluate progression free survival
- To evaluate the clinical benefit rate (CR+PR+SD>16 wks).

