6. TREATMENT PLAN

Treatment will be administered on an outpatient basis. Expected toxicities and potential risks as well as dose modifications for ABT-888 and TMZ are described in Section 7 (Expected Toxicities and Dosing Delays/Dose Modifications). No investigational or commercial agents or therapies other than those described below may be administered with the intent to treat the participant's malignancy.

A summary of the treatment plan is provided in Table 6.1 below.

A summary of on study evaluation is provided in the study calendar in Table 10.1.

In summary, all subjects who sign informed consent, enroll in the study, and meet the pre-treatment requirements will receive study drugs. Subjects will self administer ABT-888, 30mg, every 12 hours PO on days 1-7 of each 28 day cycle. Subjects will self administer TMZ, 150-200mg/m², orally once daily on days 1-5 ONLY of each cycle. The dose of TMZ will be 150mg/m² for CYCLE 1, and will increase to 200mg/m² for CYCLE 2 and higher, per section 6.2.2. The intention is for both drugs to be administered concurrently and ABT-888 and TMZ should begin on the same day. If a delay in dosing of either drug is required for any reason, both drugs should be delayed until the subject is eligible to receive both drugs as scheduled concurrently. If for any reason the subject is permanently taken off either ABT-888 or TMZ, the subject will be off study treatment. Refer to Section 6.2 for details of administration of each agent.

Table 6.1 Treatment Descriptions

*** CYCLE 1 ONLY ***					
Agent	Instructions	Dose	Route	Schedule	Cycle length
ABT-888	Take AM dose at same time as TMZ	30mg q 12 hrs	PO	Days 1-7	28 days
TMZ	Take without food	150mg/m ² QD	PO	Days 1-5	
*** CYCLE 2 and HIGHER ***					
Agent	Instructions	Dose	Route	Schedule	Cycle length
ABT-888	Take AM dose at same time as TMZ	30mg q 12 hrs	PO	Days 1-7	28 days
TMZ	Take without food	200mg/m ² QD	PO	Days 1-5	

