6.2. Agent Administration

6.2.1. ABT-888

Dosing

Total daily dose will be 30mg every 12 hours (unless modified according to dose modification instructions below) given on days 1-7 every 28 days.

ABT-888 will be supplied as 10mg capsules. Subjects will be instructed to take 3 (three) 10mg capsules to achieve the 30mg dose.

Subjects will self-administer the morning and evening doses of ABT-888 orally, approximately 12 hours apart in the same calendar day.

On days when TMZ will also be coadministered (days 1-5), the morning dose of ABT-888 and TMZ can be taken at around the same time, but the study drugs should be taken under fasting conditions to reduce the chance of nausea and vomiting per TMZ label recommendation (no food for at least 1 hour before and after dose; water and regular medications are OK). The evening dose of ABT-888 may be taken with or without food.

The following guidelines shall be used regarding missed doses of ABT-888:

- It is recommended that if a subject misses a scheduled dose of ABT-888 and less than 6 hours have passed since the scheduled dosing time, the dose should be taken immediately.
- It is recommended that if more than 6 hours have passed since the scheduled dosing time, the subject should not take the missed dose of ABT-888, but should wait and take the next regularly scheduled dose.
- If the subject vomits within 15 minutes of taking ABT-888, another dose of ABT-888 will be administered. The dose may only be repeated once.
- If the subject vomits and more than 15 minutes have passed from the time of oral dosing of ABT-888 then no additional doses of ABT-888 will be taken.
- For situations not otherwise clearly described above, the principal investigator or designee will provide appropriate instructions for subjects who miss a dose of study drug.

Criteria to treat

There are no known direct clinically significant toxicities due to ABT-888 monotherapy for which dose dependent modification of ABT-888 are necessary. Criteria to treat will be based on the criteria to treat with TMZ, described in Section 6.2.2.

Documentation of dosing

A record of ABT-888 supplied to each subject must be maintained in the source documents.

Each subject will receive a drug diary (Appendix G) to record the date, time and amount of drug taken.

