6.2.2. Temozolomide

Dosing

TMZ will be administered orally once a day for 5 consecutive days on days 1-5 and repeated every 28 days.

The dose administered will be determined using the body surface area (BSA) calculated at the beginning of each cycle. The BSA will be calculated from the height obtained at the baseline evaluation and from the weight obtained at the beginning of each cycle. The chart in Appendix B may be used to determine the dose of TMZ based on known BSA. A maximum BSA of 2.5 for TMZ dose calculation will be used for subjects with BSA>2.5.

TMZ dosing will be as follows, shown schematically in Table 6.2:

Cycle 1 Only:

[figure not shown]
The dose for the first cycle of TMZ is 150 mg/m²/day. Blood counts will be monitored day 15 and 22 for cycle 1.

Cycle 2 and higher:

The dose for cycle 2 and higher will be determined as follows:

- If during the first cycle, all clinically significant CTCAE non-hematological toxicity attributable to TMZ observed was Grade ≤ 2 (except for alopecia) and with platelets $\geq 100,000/\text{ul}$ and ANC $\geq 1500/\text{ul}$ then TMZ dose should be escalated to 200 mg/m²/day and this dose should be used as the starting dose for subsequent cycles.
- If treatment after cycle 1 has to be delayed because of ongoing clinically significant non-hematological toxicity of CTCAE grade > 2 , then no escalation is possible. If subject does not meet the criteria for dose escalation then the subject should remain at the 150mg/m²/day dose.
- If during the first cycle the subject experiences platelets $< 50,000/\text{ul}$ and/or ANC $< 1000/\text{ul}$ and/or a clinically significant non-hematologic toxicity $>$ grade 3 then subject should postpone therapy until ANC $> 1500/\text{ul}$ and platelets $>100,000/\text{ul}$ and reduce dose to 100mg/m²/day per dose reduction in Section 7.
- If the dose was not escalated at cycle 2 then the dose should not be escalated in further cycles.

Table 6.2 TMZ Dosing Modification For Cycle 2

The start of the each cycle will be scheduled 28 days \pm 3 days after the last day of the previous cycle.

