15. STATISTICAL CONSIDERATIONS

15.1. Study Design/Endpoints

This is a single arm, single stage phase II study to evaluate the response to the novel PARP inhibitor ABT-888 in combination with TMZ. Eligible subjects have unresectable or stage IV metastatic breast cancer with measurable disease according to RECIST. Subjects must have at least 1 prior therapy for metastatic disease, with no maximum. Subjects in the expansion cohort may have any number of prior chemotherapy regimens for metastatic disease, with no limit on total number of lines of prior therapy. All histologic subtypes of breast cancer are eligible. Subjects will receive study treatment with ABT-888 twice each day on days 1-7 and TMZ once each day on days 1-5 of each 28 day cycle. The primary endpoint of the study is the objective response rate. Secondary endpoints are the clinical benefit rate (CR+PR+stable disease > 16 weeks), progression free survival, and safety. Additional correlative exploratory endpoints will be carried out on archived tumor sample and blood.

There are only few small reports of TMZ for metastatic breast cancer. The reported response rate to TMZ monotherapy is poor, with 0 responses in 18 patients³². TMZ in combination with platinum in metastatic breast cancer with brain metastases was 6 of 15 patients³³, and 2 studies of TMZ monotherapy in breast cancer with brain metastases demonstrated no responses^{34, 35}. A growing literature of preclinical studies of TMZ and ABT-888 (and other PARP inhibitors) provides strong support for the hypothesis that the combination will demonstrate significant clinical activity.

Primary Endpoint

The primary endpoint of this study is to determine the objective response rate (ORR) of ABT-888 and TMZ in metastatic breast cancer.

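### Section 6.2.2 counts each cycle start from the last day of the previous cycle, which cannot give the 28-day cycle stated everywhere else; the anchor should be the first day

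*Combined protocol and SAP*

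**What the plan says.** The dosing part of Section 6.2.2 closes with the scheduling rule: "The start of the each cycle will be scheduled 28 days", with a tolerance of plus or minus "3 days after the last day of the previous cycle".

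The cycle length appears in five other statements, and all agree on 28 days:

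- Section 6.2.2, opening line, for temozolomide: "on days 1-5 and repeated every 28 days".
- Section 6.2.1, for ABT-888: "given on days 1-7 every 28 days".
- Section 6: "every 12 hours PO on days 1-7 of each 28 day cycle". Table 6.1 lists a cycle length of 28 days.
- Section 2.1: "every 12 hours on days 1 through 7 of each 28 day cycle".
- Section 15.1: "TMZ once each day on days 1-5 of each 28 day cycle".

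Two further places imply the same length. Section 2.1 states "Measurable tumor will be assessed for response every 8 weeks", while Section 11 asks for re-evaluation every two cycles, so one cycle is four weeks. The phase 1 schedule described in Section 3.3 is 7 days of ABT-888 followed by 21 days of rest, again 28 days.

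**The concern.** A 28-day cycle means 28 days from one Day 1 to the next. The rule in Section 6.2.2 starts its 28-day count at the end of the previous cycle, so the start-to-start interval must be longer than 28 days.

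This is the only sentence that says how to place a cycle start relative to the previous cycle, with a tolerance. Section 10 adds a general ±3 days, but around the date the protocol specifies, and this sentence specifies the wrong date. A patient restarted on day 29, as the rest of the protocol intends, would be outside the window as written. A patient scheduled by the sentence would be dosed too late. Scan timing follows cycle starts (Section 10, footnote k), so a late cycle 3 would also move the first response assessment.

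**Working it through.** **Inputs.** The 28 ± 3 day gap is from Section 6.2.2. ABT-888 is given on days 1–7 and temozolomide on days 1–5 (Section 6). Cycle length is 28 days (Table 6.1). Follow-up scans fall 0–14 days before each odd-numbered cycle (Section 10, footnote k), and tumour assessment is every 8 weeks, or 56 days (Section 2.1).

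**Formulas.** Day 1 is the cycle start.

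- Next Day 1 = anchor day + 28 (± 3).
- Interval = next Day 1 − 1.
- Cycle 3 start = 2 × interval, in days after cycle 1 Day 1.
- First scan window = cycle 3 start − 14 to cycle 3 start.

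**Which anchor reproduces 28 days?** Scan windows in the table use the nominal interval.

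| Anchor | Next Day 1 falls on | Interval in days (±3) | Cycle 3 start | First scan window |
|---|---|---|---|---|
| Day 28, last day of the cycle | 28 + 28 = 56 | 55 (52–58) | 110 | 96–110 |
| Day 7, last ABT-888 dose | 7 + 28 = 35 | 34 (31–37) | 68 | 54–68 |
| Day 5, last temozolomide dose | 5 + 28 = 33 | 32 (29–35) | 64 | 50–64 |
| Day 1, first day of the cycle | 1 + 28 = 29 | 28 (25–31) | 56 | 42–56 |

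Only the first-day anchor returns 28 days, and two such cycles are 56 days, which matches the 8-week assessment. None of the three last-day windows contains 28; the closest, from day 5, begins at 29. The ±3 tolerance therefore does not absorb the error.

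**Which last-day reading is natural?** The calendar has blood counts on days 15 and 22, so a cycle does not end on day 5 or 7. Section 13.1.2 also sets form deadlines from the last day of the cycle, which most naturally means its end. The natural reading is day 28, the one furthest from 28 days. It adds 55 − 28 = 27 days per cycle, more than the 3-week (21-day) limit on toxicity delay in Section 7.2.

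**Effect on the first scan.**

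- Day-28 anchor: cycle 3 starts 104 to 116 days after cycle 1 Day 1 (2 × 52 to 2 × 58). The earliest scan is at 104 − 14 = 90 days, which is 90 − 56 = 34 days after week 8.
- Day-7 anchor: the nominal window (54–68) contains day 56. With the full +3 days in both cycles, cycle 3 starts at 2 × 37 = 74 and the window is 60–74, which misses it.
- Day-5 anchor: even with +3 in both cycles, cycle 3 starts at 2 × 35 = 70 and the window, 56–70, still includes day 56.

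**Hypothetical worst case.** If the day-28 reading were followed in every cycle, dose intensity would be 28/55 = 50.9% of plan (28/58 = 48.3% to 28/52 = 53.8%). This bounds the error and is not an expected effect.

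**The case against.** The best defence is that the rest of the protocol leaves no real doubt. Table 6.1 has a cycle-length entry of 28 days for cycle 1 and for later cycles, and four other sections and the opening of Section 6.2.2 itself agree. The literal reading would leave a gap of about 27 days after day 28 that no other section provides for. The study runs within a single cancer center, and nothing in the documents shows that any patient was dosed at another interval. The largest figures, for dose intensity and the latest scan dates, come from a reading that sites are unlikely to adopt.

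All of that stands, and it limits the weight of the point. It does not rescue the sentence: no definition in the protocol makes the last day yield 28 days, and the more lenient last-dose readings also miss.

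The defence can also say that changing the anchor is not the only repair. Dropping the anchor and relying on the 28-day cycle with Section 10's general ±3 days would remove the conflict too. That is correct, and the choice between the two is one of drafting.

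**Conclusion.** The sentence is wrong as written. It gives a start-to-start interval of 55, 34 or 32 days, depending on what the last day means, against the 28 days stated elsewhere. It is probably a slip for the first day.

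The severity is minor. This assumes that sites follow the 28-day statements, which is likely but not guaranteed by the text. At nominal intervals, only the day-28 reading pushes the first scan past week 8. Section 3.3 reports the 41 primary-study patients as already enrolled, so a correction mainly serves the expansion cohort of about 20 patients (up to 22, Section 15.2). Sample size, decision rules and error rates are unaffected.

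**What to change.** In the scheduling sentence of Section 6.2.2, replace the last day with the first day (Day 1) of the previous cycle, and keep the 28 days and the ±3-day tolerance. This restores an interval of 28 days (25 to 31) and agrees with every other statement of cycle length. Section 10 needs no change. The cost is one phrase in a protocol amendment, with no added visits, procedures or patients.

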Capsules of TMZ are available in 5, 20 and 100 mg strengths. The daily dose will be rounded to the nearest 5 mg. However, for patient convenience the dose may be rounded up or down no more than 5% from calculated dose in order to minimize the number of pills per dose. The exact dose administered should be recorded in the CRF. Each daily dose should be given with the least number of capsules. Appendix C may be used to assist in calculating to capsule combinations to achieve the desired dose. Subjects will be instructed to fast for at least one hour before and one hour after administration of TMZ. Water is allowed during the fast period. Subjects should be told to swallow the whole capsules in rapid succession without chewing them. If vomiting occurs during the course of treatment, no re-dosing of the subject with TMZ is allowed before the next scheduled dose. Missed doses will not be made up. For situations not otherwise clearly described above, the principal investigator or designee will provide appropriate instructions for subjects who miss a dose of study drug.

Please see Section 7 for dose modification guidelines.

Criteria to Treat

Prior to each 5-day treatment with TMZ a complete blood count (CBC) must be obtained (within -3 days prior to dosing, except for cycle 1 which may be -7 days). Blood counts will be evaluated again day 15

and 22 for cycle 1 and on day 22 for cycle 2 and higher. Within -3 days prior to first dose of each 5-day TMZ treatment the subject must have an ANC \geq 1500/ μ l and platelet count \geq 100,000/ μ l. On day 1 of each cycle (within -3 days) all clinically significant treatment related non-hematological toxicity grade 3 or 4 (except for alopecia) must have resolved (CTCAE grade \leq 1). If toxicity persists, treatment should be delayed by about one week for up to 3 consecutive weeks. If after 3 weeks of delay all clinically significant treatment related toxicity has still not resolved then subject should be discontinued from study treatment.

Documentation of dosing

A record of TMZ supplied to each subject must be maintained in the source documents.

Each subject will receive a drug diary ([Appendix G](#)) to record the date, time and amount of drug taken.

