7.2. Dose Modifications/Delays

Blood counts will be evaluated within -3 days prior to day 1 of each cycle. Subject must have an ANC \geq 1500/ μ l and platelet count \geq 100,000/ μ l within -3 days of day 1 of each cycle. On day 1 of each cycle (within -3 days) all clinically significant treatment related **non-hematological** toxicity grade 3 or 4 (except for alopecia) must have resolved (CTCAE grade \leq 1 or baseline). If toxicity persists, treatment should be delayed for up to 3 consecutive weeks. If after 3 weeks of delay all clinically significant treatment related toxicity has still not resolved then any further treatment with TMZ and ABT-888 should be stopped (subject is off treatment). Study drug interruptions for events that are clearly not related to the study drug, e.g., underlying cancer, planned surgical procedures or acute viral illnesses, should not necessitate a dose reduction and treatment may be delayed as necessary beyond 3 weeks.

Dose reductions:

ABT-888 Dose Reduction and Delay

The following are guidelines for dose reduction, delay and discontinuation of ABT-888.

- ABT-888 dose reduction and delay guidelines are summarized in Table 7.2.1.
- ABT-888 should be discontinued at the same time of discontinuation of TMZ.
- For any subject who experiences Grade 3/4 toxicity which is not attributable to TMZ or the underlying disease, the ABT-888 dose will be discontinued until the toxicity resolves to Grade 1 or lower or to baseline if Grade 2 at the time of study entry. The dose of ABT-888 will be reduced to a dose of 20 mg every 12 hours. Only one ABT-888 dose reduction is allowed. If a subject experiences a second Grade 3/4 toxicity which is not attributable to TMZ or the underlying disease and is thought (by the treating physician with consultation of the principal investigator as needed) to be related to the ABT-888, subject must discontinue study treatment.

- Any event of seizure, regardless of grade or attribution, requires interruption of ABT-888 and discussion with the Principal Investigator regarding the decision to resume treatment, and the Abbott Oncology Safety Desk (Section 12.5.1) should be notified.

Temozolomide Dose Reduction and Delays

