Clinically significant hematological toxicities should result in TMZ dose reduction or delay. During treatment, CBCs should be monitored and the next cycle of therapy should not be started unless the ANC is $> 1500/\mu\text{L}$ and platelet count is $> 100,000/\mu\text{L}$. For any Grade 3/4 toxicities attributable to TMZ, dose reduction and/or delay guidelines should be followed per Table 7.2.1. Dose reductions in the next cycle should be based on lowest blood counts and worst non-hematologic toxicity observed in the previous cycle. The $75 \text{ mg/m}^2/\text{day}$ dose is the lowest dose of TMZ that is allowed in this study. Subjects must stop TMZ and ABT-888 if they are at the $75 \text{ mg/m}^2/\text{day}$ dose level of TMZ and require an additional dose reduction (per Table 7.2.1) due to toxicities. Temozolomide dose levels to be used for dose reductions are summarized in Table 7.2.2.

For TMZ dosage calculations based on body surface area please refer to Appendix B.

Important:

- If the dose was **reduced or delayed** for toxicity, there will **be no dose re-escalation**.
- Any event of seizure that was clearly attributable to ABT-888 requires discontinuation of ABT-888.

Table 7.2.1 ABT-888 and TMZ Dose Reduction or Delay

	Adverse Event	Dose Reduction
Hematologic Toxicity attributable to TMZ	ANC < 1000/ μ L* and/or Platelets < 50,000/ μ L*	
 1. Hold TMZ and ABT-888. Check CBC weekly until recovery to: ANC > 1500/μL and platelets > 100,000/μL and 2. Reduce TMZ dose by 1 dose level at the next cycle***
	ANC 1000/ μ L* to 1500/ μ L* Platelets 50,000/ μ L* to 100,000/ μ L*	
 1. Hold TMZ and ABT-888. Check CBC weekly until recovery to ANC > 1500/μL and platelets > 100,000/μL and 2. Maintain Current TMZ Dose at the next cycle
Non-hematologic Toxicity attributable to TMZ	Nausea/Vomiting CTC \geq Grade 3 despite optimal antiemetic therapy	
 1. Delay cycle until Grade 1 (or Grade 2 if present at baseline) and 2. Reduce TMZ dose by 1 dose level for the next cycle***
	Fatigue, constipation, anorexia or headaches CTC \geq Grade 3	
	Any other CTC \geq Grade 3 deemed to be clinically significant by PI	
	Adverse Event	Dose Reduction**

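### Section 6.2.2 and Section 7.2 with Table 7.2.1 set different recovery grades for starting the next cycle, so a patient with a baseline Grade 2 symptom can be restarted under one and stopped under the other

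*Combined protocol and SAP*

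**What the plan says.** **Non-hematological recovery.** Section 6.2.2, under Criteria to Treat, requires that on day 1 of each cycle "all clinically significant treatment related non-hematological toxicity grade 3 or 4 (except for alopecia) must have resolved", with CTCAE Grade 1 or lower given in parentheses as the meaning of resolved. It makes no allowance for the grade at entry. The first paragraph of Section 7.2 repeats the sentence with a longer parenthesis: "except for alopecia) must have resolved (CTCAE grade \leq 1 or baseline". The ABT-888 bullet in Section 7.2 asks for recovery to "Grade 1 or lower or to baseline if Grade 2 at the time of study entry". Table 7.2.1, in its non-hematological and ABT-888 rows, says "Delay cycle until Grade 1 (or Grade 2 if present at baseline".

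**Consequence of non-recovery.** Section 6.2.2 states: "If after 3 weeks of delay all clinically significant treatment related toxicity has still not resolved then subject should be discontinued from study treatment". Section 7.2 has the same 3-week limit and then stops both drugs.

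**Blood counts.** Criteria to Treat in Section 6.2.2 and the opening of Section 7.2 ask for ANC of at least 1500/µL and platelets of at least 100,000/µL. The TMZ paragraph of Section 7.2 says that "the next cycle of therapy should not be started unless the ANC is" above 1500/µL and the platelet count above 100,000/µL. Table 7.2.1 has a hold row that runs up to those two values and releases the patient only above them. The cycle 1 low-count bullet in Section 6.2.2 also asks for values above them.

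**The concern.** The two sections give nearly the same instruction for the same decision on the same day, but define recovery differently. Because both attach a 3-week stop to that definition, the difference reaches beyond timing: it can decide whether a patient stays on treatment.

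The wording of Section 7.2 and its table shows that the authors expected some patients to enter with a Grade 2 finding. Eligibility sets no limit on prior lines of therapy and admits ECOG performance status up to 2 (Section 4.1), so such patients are plausible. A site following either section would deviate from the other. Section 15.3 plans to report early withdrawals due to adverse events, and for these patients that tally could depend on which page the site applied.

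**Working it through.** The plan states no figure on this point and no formula applies. The check is to apply each rule to the same patient.

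**Patient A.** Grade 2 symptom at baseline, clinically significant treatment-related Grade 3 during a cycle, back to Grade 2 by the next day 1, counts adequate.

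| Place | Grade that counts as recovered | Patient A |
|---|---|---|
| Section 6.2.2, Criteria to Treat | 1 or lower | Held; discontinued if still Grade 2 after 3 weeks |
| Section 7.2, opening paragraph | 1 or lower, or baseline | May start |
| Section 7.2, ABT-888 bullet (toxicity not attributed to TMZ or the disease) | 1 or lower, or baseline if that was Grade 2 | May restart |
| Table 7.2.1 | 1, or 2 where Grade 2 existed at baseline | May start |

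The main contrast is Section 6.2.2 against the other three. Within Section 7.2, the opening paragraph puts no cap on the baseline grade, while the bullet and table stop at Grade 2. They differ from one another only if the baseline grade was above 2.

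**Patient B.** ANC exactly 1500/µL or platelets exactly 100,000/µL on day 1, the other count above its limit, no other toxicity.

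| Place | Inequality | Patient B |
|---|---|---|
| Section 6.2.2, Criteria to Treat | at or above | May start |
| Section 7.2, opening paragraph | at or above | May start |
| Section 7.2, TMZ paragraph | strictly above | Not started |
| Table 7.2.1 | hold row includes the limit; release strictly above | Held, weekly CBC |
| Section 6.2.2, cycle 1 low-count bullet (recovery after low counts) | strictly above | Not released, where this bullet applies |

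The inequality therefore changes within each section as well as between them.

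**Patient C, as a control.** Baseline Grade 1 or lower, toxicity back to Grade 1 or lower, both counts above the limits. Every text allows the cycle to start.

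**Which text governs.** Section 6.2.1 bases the ABT-888 criteria to treat on Section 6.2.2. Section 6.2.2 refers to Section 7 for dose modification, and the introduction to Section 7 refers delays to Section 7.2. Neither section is said to override the other on criteria to treat.

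**The case against.** The case for treating this as a light edit has several parts.

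- **The conflict is narrow.** Discontinuation under Section 6.2.2 needs a baseline Grade 2 symptom, worsening to a clinically significant treatment-related Grade 3 or 4, return to Grade 2 and no further improvement through 3 weeks of delay. This stands.
- **The 3-week stop is not peculiar to Section 6.2.2.** This also stands. Only the definition of recovery differs.
- **Sites are sent to Section 7 for modifications and delays.** This is true, but Section 6.2.1 sends ABT-888 back to Section 6.2.2, so the cross-references do not settle the question.
- **A symptom back at its pre-study grade is arguably no longer treatment-related toxicity,** since Section 12.2.1 defines an adverse event by onset or worsening after treatment starts. This softens the conflict, but Section 6.2.2 states an absolute grade and Section 7.2 adds the baseline allowance in words.
- **Few patients are likely to qualify.** Section 3.3 reports thrombocytopenia and neutropenia as the most common Grade 3/4 toxicities, and the non-hematological rule does not cover them. Exclusion 4.2.1 removes patients who have not recovered from adverse events of earlier agents. Both points stand.
- **The count mismatch is editorial.** It matters only at the exact limits, and is rightly a minor point.

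A reader might go further and put a number on this, for example 5–10% of 41 + 20 = 61 patients, or about 3 to 6. The documents do not support that. They give no rate of baseline Grade 2 symptoms or of the later course required. In addition, Section 3.3 describes the 41 as already enrolled, so an amendment cannot change cycle starts already made for them. The same assumed share of the 20 to 22 expansion patients (Section 15.2) would be 1.0 to 2.2, but the share itself remains a guess.

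**Conclusion.** The contradiction is real and stands in the current text. For a patient with a baseline Grade 2 symptom that worsens to a treatment-related Grade 3 or 4 and returns to Grade 2, Section 7.2 and Table 7.2.1 permit a restart. Section 6.2.2 requires a hold, then discontinuation if the symptom is still Grade 2 after 3 weeks. The count inequality is a secondary inconsistency that affects only values exactly at the limits.

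The number of patients affected cannot be derived. It is probably small, given the chain of conditions, exclusion 4.2.1 and the mainly hematological toxicity seen so far. Looking forward, it concerns mainly the expansion cohort, assuming that few of the 41 primary-study patients still have cycles to start.

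A reader might also infer that the response-rate result is biased, because the success thresholds are small counts (5 of 41 and 7 of 20 in Section 15.1). Nothing in the documents shows this. Section 15.4.2 keeps eligible treated patients in the response analysis despite errors in schedule or administration, and no direction or size of effect can be calculated. What is shown is a conflict over patient management, which can carry into exposure and into the count of withdrawals due to adverse events.

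**What to change.** Reconcile the cycle 1 low-count bullet and Criteria to Treat in Section 6.2.2, the opening paragraph, ABT-888 bullet and TMZ paragraph of Section 7.2, and Table 7.2.1. Together they should state one recovery grade, one baseline allowance (including whether it has a cap) and one inequality for ANC and platelets. The hold row of the table should not overlap the values that permit a start. Stating the rule once and cross-referring to it elsewhere would keep the sections from diverging again. The clinical team must decide which rule applies; this review does not propose one.

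The cost is wording in an amendment. Sample size, endpoints and the analysis plan are unaffected.
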